6.3 Missing Data

Missing values will be primarily due to children lost to follow-up and not reached at Day 7 and Day 28.

The primary analysis will be performed assuming the best case scenario (alive and not hospitalised) for children lost to follow-up or withdrawn.

As described in Section 6.2.4, a set of sensitivity analysis will be performed in case of substantial missing data on the primary outcomes (e.g. >10%). Missing data will be treated as outline below:

- ξ Worst case scenario: children lost to follow-up or withdrawn will be assumed as dead or hospitalised.
- ξ Complete cases: children lost to follow-up or withdrawn will be excluded.
- ξ Multiple imputations with chained equations: under the assumption that children are lost to follow-up or withdrawn at random, chained equations with 50 imputed dataset, separately by treatment group, will be used. Relevant baseline characteristics and all available follow-up data will be used to impute death and hospitalisation (both primary and secondary) as binary variables.

Additionally, missing data will be described by arm and by relevant indicators, such as referral and severe disease to visually inspect for imbalances.

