Caregivers will be offered several options for completing follow-ups at Day 7 and Day 28. Follow-up will be conducted remotely when possible. For caregivers who can provide a phone number at the day of enrolment, Day 7 and Day 28 follow-ups will be conducted by phone. If the initial phone call fails and the phone number is valid, at least three attempts will be made on subsequent three days at different times of the day to try to reach the caregiver. If the phone number is not valid, no other call attempts will be made and alternative follow-up options will be initiated if consented for. Except during the initial phone call, follow-up can be carried out with a caregiver other than the one who gave consent at the day of enrolment if this person is able to provide information about the child. For caregivers who cannot provide a phone number at the day of enrolment, community mechanisms will be relied on to arrange a call with the caregiver through a community focal person, e.g. a community health worker (CHW) or a community leader. To this aim, CHWs and community leaders in the targeted study areas will be asked for their consent to have their phone numbers shared with RAs in order to contact caregivers without a phone for their Day 7 and Day 28 follow-ups. Independently on whether they provided a phone number or not, caregivers will be given the alternative option to consent for in-person Day 7 follow-up that will have to be conducted as soon as possible after all remote attempts failed. In-person Day 7 follow-ups could be conducted either at the caregiver's household or another specified community location.. If Day 7 follow-up has been unsuccessful, Day 28 follow-up will still be attempted. During both Day 7 and Day 28 follow-ups, a structured questionnaire will be administered to assess the primary and secondary outcomes, including details of any government or private hospital admission. In case of non-recovery, if the child is still at home, the study team will advise the family to return to the PHC clinic for a follow-up consultation.

Additionally, visit information from government-designated hospital records will be collected retrospectively for children reported to have attended hospital by the caregiver at follow-up or referred at day 0 and lost to follow-up including clinical assessment on arrival (vital signs, admitting diagnosis), admission details (duration, if oxygen was administered, intensive care

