8.2.4 Data quality assurance and control

Quality assurance activities across all studies will be more intense during study start-up to ensure quality data practices are instituted from the start of the trial. Further details will be given in the DMP and SOPs.

All research assistants will be trained to provide information and seek written consent using the information and consent form. Separate trainings will cover all aspects of quantitative data collection and all aspects of qualitative data collection. A competency assessment using scenarios will be done before commencing field work.

Data reconciliation between the different visits of the same child will be one of the most crucial data quality activity in the pragmatic cluster RCT. Specific procedures will be developed for this purpose. To identify repeat visits of children that may re-attend the study facility where they enrolled or any other study facility during the follow-up period, participants will be given a study card (or sticker) with a unique ID number. Retrospective search for data at referral level will be restricted to facilities within the geographical area where the study is running and will be targeted to include only children reported to have attended hospital by the caregiver at follow-up and referred children lost to follow-up. The name of the referral facility will be requested during the follow-up call. If available, it should further restrict the scope of the search and the probability of negative matches when cross-checking the participant identity. Children who re-attend any study facility more than 28 days after their previous enrolment will be enrolled for the new disease episode and given a new ID number. If available, the old ID number will be recorded to facilitate linking of the different disease episodes. Data to be potentially reconciled will be flagged by automated cross-check of a set of personal identifiers. Given that

personal identifiers may not be identically recorded at each visit, fuzzy matching methods will be used to calculate a score of similarity between records and likelihood that they relate to the same child. Reconciliation of records with high similarity scores will be manually validated.

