6.1.1 General definitions

Day 7 / Day 28 assessment

Day 7 / Day 28 assessment refers to information reported by the caregiver after Day 0 and recorded in Day 7 / Day 28 forms. Data collected as part of unscheduled visits are also integrated in these forms.

If multiple successful follow-up assessments for the same child are recorded within Day7 or Day28 databases, the most recent follow-up assessment within each database will be used. To limit potential recall bias, assessments conducted far beyond the expected follow-up time will be dropped. This will be 30 and 60 days from Day 0 for Day 7 and Day 28 respectively.

Death

A child will be considered deceased if, from Day 7 / Day 28 assessment, his/her status at the time of follow-up is “deceased”. In case of implausible death date (i.e. prior to enrolment date), death will be handled as follow:

- ξ if death date is recorded at Day7 follow-up, death will be assumed to be within 7 days of Day0
- ξ if death date is not recorded at Day7 follow-up but only at Day28 follow-up, death will be assumed to be after 7 days of Day0 but within 28 days.

Hospitalisation

A child will be considered hospitalised if, from Day 7 / Day 28 assessment, he/she went to a hospital, was admitted overnight or if his/her status at the time of follow-up is “hospitalised”. In case of implausible hospitalisation date (i.e. prior to enrolment date), hospitalisation will be handled as follow:

- ξ if hospitalisation date is recorded at Day7 follow-up, hospitalisation will be assumed to be within 7 days but after 24hrs of Day0
- ξ if hospitalisation date is not recorded at Day7 follow-up but only at Day28 follow-up, hospitalisation will be assumed to be after 7 days of Day0 but within 28 days.

Hospitalisation within 24hrs of Day0

For the purpose of primary analysis, a child will be considered admitted to hospital 24hrs of Day0 consultation if the date of hospitalisation is the same as Day0 date or is one day after Day0 date.

Referral

A child will be considered to be referred (either to a hospital or to an inpatient part of a larger primary healthcare facility) if, at Day0, the caregiver confirms that the child was urgently referred or the research assistant confirms that an urgent referral advice was recorded for the child. If urgency is unknown from both sources, referral will be assumed to be urgent.¹

Antibiotics

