6.1.2 Health, hospitalisation and referral outcomes

6.1.2.1 Proportion of children with a severe complication by Day 7

Severe complication is defined as death or secondary hospitalisation. Secondary hospitalisation refers to any delayed hospitalisation (occurring at any point greater than 24hrs after the Day 0 consultation) and any hospitalisation occurring without a referral.

Information on death and hospitalisation will be taken, in order, from:

- ξ Day7 follow-up assessment
- ξ If Day7 follow-up assessment is missing, Day28 follow-up assessment

Death will be counted in the numerator if death date is within 7 days of Day0 (7th day included). Hospitalisation will be counted in the numerator if the child was not referred at Day0 or hospital admission date is within 7 days of Day0 (7th day included) but after 24hrs of Day0.

The denominator will be all children recruited. Children for whom no death and hospitalisation data are available or withdrew prematurely from the study will be assumed to be alive and not hospitalised by Day7.

6.1.2.2 Proportion of children with a severe complication by Day 28

Severe complication is defined as per the outcome above.

Information on death and hospitalisation will be taken, in order, from:

- ξ Day7 follow-up assessment
- ξ If Day7 follow-up assessment is missing or no outcomes were reported, Day28 follow-up assessment
- ξ If both Day7 and Day28 assessments are missing or no outcomes were reported, unscheduled visits (deaths only)

Death will be counted in the numerator if death date is within 28 days of Day0 (28th day included). Hospitalisation will be counted in the numerator if the child was not referred at Day0 or hospital admission date is within 28 days of Day0 (28th day included) but after 24hrs of Day0.

The denominator will be all children recruited. Children for whom no death and hospitalisation data are available or withdrew prematurely from the study will be assumed to be alive and not hospitalised by Day28.

6.1.2.3 Proportion of children admitted to hospital within 24 hours of Day 0 consultation and as a result of a referral

Information on hospitalisation will be taken, in order, from:

- ξ Day7 follow-up assessment
- ξ If Day7 follow-up assessment is missing, Day28 follow-up assessment

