Hospitalisation will be counted in the numerator only if the child received a referral advice (as per definition above) at Day0 and hospital admission date is within the end of the following day. The denominator will be all children recruited.

Additionally, the proportion will be calculated and reported using only children who were referred as denominator.

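### Both primary outcomes score children missed at Day 7 and Day 28 as having no event, and the hospital records sought for referred-and-lost children have no stated use in them

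*SAP*

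**What the plan says.** **Sources.** SAP 6.1.2.1 (severe complication by Day 7) and 6.1.2.3 (admission within 24 hours as a result of referral) list the same two sources in order. The first is the Day 7 assessment; the second is "If Day7 follow-up assessment is missing, Day28 follow-up assessment". SAP 6.1.1 says that an "assessment refers to information reported by the caregiver after Day 0 and recorded in Day 7 / Day 28 forms", and adds that unscheduled-visit data are integrated in those forms. Hospital records are not named. The only SAP outcome that names them is oxygen at hospital (6.1.5.4).

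**Missing outcomes.** SAP 6.3: "The primary analysis will be performed assuming the best case scenario (alive and not hospitalised) for children lost to follow-up or withdrawn". SAP 6.1.2.1 repeats this for severe complication: "Children for whom no death and hospitalisation data are available or withdrew prematurely from the study will be assumed to be alive" and not hospitalised. SAP 6.1.2.3 has no such sentence, so 6.3 governs it. Both denominators are all recruited children.

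**Records collected.** Protocol 6.5.1 has hospital visit data collected retrospectively for "children reported to have attended hospital by the caregiver at follow-up or referred at day 0 and lost to follow-up". Protocol 8.2.4 restricts the search to "only children reported to have attended hospital by the caregiver at follow-up and referred children lost to follow-up". Protocol 8.1.1 describes a narrower search, limited to children reported as hospitalised between Day 0 and Day 7.

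**Other planned analyses.** SAP 4.3 plans the primary outcomes on a complete-case set as well, with no condition. SAP 6.2.4 and 6.3 add worst case and multiple imputation (50 datasets, by arm) only if missing data are substantial, with more than 10% as the example. Protocol 8.3.1 lists best and worst case among sensitivity approaches; the SAP makes best case primary and gives no reason.

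**The concern.** Events are expected in about 1% of children, so a rule that turns unknown outcomes into non-events acts directly on a small numerator. It also treats those outcomes as known.

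The gap is sharpest for admission after referral. That outcome counts an admission under a strict condition: "Hospitalisation will be counted in the numerator only if the child received a referral advice". A lost child who was not referred is therefore a known non-event. The unknown outcomes are confined to children referred and then lost, which is the group whose records Protocol 6.5.1 and 8.2.4 have searched. The data that could settle many of them have no stated role.

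The label also fails here. Alive and not hospitalised is the favourable value for severe complication. The intervention is meant to increase admission after referral, so for that outcome it is the unfavourable value. The SAP's worst case (dead or hospitalised) is unclear for the same reason.

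Either primary outcome can make the trial positive (SAP 4.1), so the rule bears on the main conclusion.

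**Working it through.** **1. Trace one child.** The child is referred at Day 0, admitted that evening, missed at Day 7 and Day 28, and the admission is found in the hospital register. Under Protocol 6.5.1 the admission is in the trial data. Under SAP 6.1.2.3 neither listed source exists. Under SAP 6.3 the child is not hospitalised and adds 0 to the numerator and 1 to the denominator. A child missed only at Day 7 is recovered from the Day 28 form and is not affected.

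**2. Reproduce the plan's figure (Tanzania).** Inputs from Protocol 6.6.1 are 80% power, alpha 0.05 (taken as two-sided), ICC 0.001, 1,680 children per cluster, 22 clusters per arm, severe complication 1.1% v 0.77%, and admission 1.5% v 1.95%.

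- n per arm = [1.96 √(2p̄(1−p̄)) + 0.842 √(p1(1−p1)+p2(1−p2))]² / (p1−p2)², which gives 13,351 (severe complication) and 13,141 (admission).
- Design effect = 1 + 1,679 × 0.001 = 2.679.
- Clusters = 13,351 × 2.679 / 1,680 = 21.3, so 22; for admission, 21.0.
- With 22 clusters (36,960 per arm, effective 36,960 / 2.679 = 13,796), power is 81.3% and 81.9%.

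The stated 22 is reached with no allowance for loss.

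**3. Equal loss d in both arms, unrelated to outcome (assumed).** Under the SAP rule each rate becomes p(1−d) with all children still in the denominator. Under complete case the rates stay and the cluster size becomes 1,680(1−d). At d = 10% that is 1,512, with design effect 2.511 and effective n of 22 × 1,512 / 2.511 = 13,247.

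| Severe complication | Rates, SAP rule | Risk difference (points) | Power, SAP rule | Power, complete case |
|---|---|---|---|---|
| d = 0 | 1.10% v 0.77% | 0.330 | 81.3% | 81.3% |
| d = 3% | 1.067% v 0.747% | 0.320 | 80.1% | 80.8% |
| d = 10% | 0.99% v 0.693% | 0.297 | 77.1% | 79.7% |

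For admission at d = 10%, the rates are 1.35% v 1.755%, the difference falls from 0.45 to 0.405 points, and power falls from 81.9% to 77.7%. About 55 of 554 control admissions (36,960 × 1.5% × 10%) and 72 of 721 intervention admissions (36,960 × 1.95% × 10%) would be scored as none. Records could restore at most these.

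**4. Unequal loss, no true effect (assumed 8% control, 12% intervention).**

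- Loss unrelated to outcome: the SAP rule gives a risk ratio of 0.88 / 0.92 = 0.957 on either outcome. Complete case gives 1.00.
- Lost children at twice the risk (2.2% v 1.1%, assumed): the SAP rule gives (1.1 − 0.12×2.2) / (1.1 − 0.08×2.2) = 0.836 / 0.924 = 0.905. Complete case gives (0.836/0.88) / (0.924/0.92) = 0.950 / 1.004 = 0.946.

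Reversing the arms reverses the direction. Higher loss in an intervention arm flatters it on severe complication and counts against it on admission.

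**The case against.** The strongest reply is that the plan already holds the main safeguard. SAP 4.3 commits to a complete-case analysis of both primary outcomes whatever the amount missing, and SAP 6.3 has missingness described by arm, referral and severe disease. Unscheduled visits are already integrated in the forms. Basing the primary outcomes on follow-up agrees with Protocol 8.1.1, so the SAP does not depart from the protocol. All of this stands, and it lowers the weight of the point. None of these analyses names hospital records as a source, however, and the headline result still rests on the rule in 6.3.

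A reader might take 10% as the expected loss, because Protocol 6.4.1 asks for 90% reach. The documents do not support that. It is a pilot criterion for phone contact at Day 7, whereas a child is missing here only if missed at both contacts, after repeat calls, community contacts and an in-person Day 7 option. At 3% loss the power cost is about one point.

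A reader might also infer that the rule biases the trial because an arm that refers more has more admissions discarded. Uneven counts alone do not do this. With equal loss the risk ratios are unchanged (0.693/0.99 = 0.70; 1.755/1.35 = 1.30) and only the risk differences shrink. A false effect needs loss that differs by arm or relates differently to outcome.

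Two further objections stand and shape the fix. Complete case is not a full cure: under severity-related loss, 5.4 of the 9.5 points of apparent reduction remain. And records exist only for referred children. For severe complication they would add delayed admissions and in-hospital deaths among referred children but nothing for lost children who were not referred, so an arm that refers more would be ascertained more fully.

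**Conclusion.** The point holds on the text: a documented admission after referral, in a child missed at both contacts, would be analysed as no admission, and best case is the wrong label for one of the two primary outcomes. This should be fixed before the final analysis by arm.

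Its size cannot be fixed from the documents, which give no loss rate, no balance of loss between arms and no record-match rate. On assumed values, the fair power comparison at 10% equal loss is 77.1% (SAP rule) against 79.7% (complete case), about 2.6 points. The comparison with 81.3% at no loss includes a cost that no method avoids without recovering the missing outcomes. The bias is 0.957 against a true 1.00 for 8% v 12% loss unrelated to outcome. These figures assume equal cluster sizes, an ICC of 0.001 and alpha 0.05.

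The documents do not show that the trial's result will be biased, or in which direction.

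**What to change.** 1. **SAP 6.1.2.3:** add hospital records as a third source for referred children with no successful Day 7 or Day 28 assessment, and report by arm how many are matched. Reconcile Protocol 8.1.1 with 6.5.1 and 8.2.4 on whose records are searched; if the narrower search was the one used, this source may not exist.
2. **SAP 6.3:** make multiple imputation, already specified by arm, the primary handling of outcomes still missing, and include referral status among the predictors. For the admission outcome, impute only for referred-and-lost children, because non-referred children are known non-events. Keep all-lost-as-no-event, complete case and worst case as sensitivity analyses without the 10% trigger. Define best and worst case separately for each outcome.
3. **SAP 6.1.2.1:** report severe complication with and without hospital records, because their coverage follows referral and may differ between arms.

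The cost is SAP wording and some programming. No new data collection is needed if the search in Protocol 6.5.1 and 8.2.4 was carried out. The price is a missing-at-random assumption, which the retained sensitivity analyses would test.

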- Proportion of children prescribed an appropriate antibiotic at Day 0 consultation

Sub-group analyses will include age (under 2 months, 2 – 12 months, 13 – 59 months), sex, and clinical presentation (with cough / difficulty breathing, fever, other). Other exploratory analysis will be conducted of individual and health system factors associated with health and patient-centred outcomes.

Mixed methods sub-studies will mostly be exploratory, to evaluate quality of care outcomes and explore perceptions, values, attitudes and beliefs. Process evaluation criteria will be evaluated according to the Medical Research Council criteria.

Cost and modelled cost-effectiveness will assess:

- Full implementation cost of the intervention per focal country (cost to health system as well as direct costs paid by the household to the health system)
- Cost per child assessed using pulse oximetry devices and CDSA per country; where applicable, compared to cost per child in routine care
- Modelled cost per DALY averted attributed to the introduction of pulse oximetry and CDAs

Sample size

The sample size for the pragmatic cluster RCT is calculated separately for each country to compare each of the intervention arms with the control arm. In order to detect a 30% reduction in the severe complication primary outcome (from 1.1% to 0.77%) with 80% power, we estimate a sample size in each country as follows:

- India – Initial sample size calculation for the three arm trial was 0 facilities per arm, recruiting an average of 510 children over the 12 month period, with an average of 110 per CHC per month and 20 children per PHC, and a facility ratio of CHC : PHC of 1:3, equating to 20,400 children per arm over the study. Following the decision not to introduce the CDSA plus pulse oximetry arm, a decision was made to reallocate facilities to the remaining two arms up to 60 facilities per arm.
- Tanzania – 22 facilities per arm, recruiting an average of 1680 children over the 12 month period, with an average of 350 per health centre per month and 70 per dispensary per month, and an average ratio of health center : dispensary of 1:3, equating to 36,960 children per arm over the study

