6.4 Outcomes

6.4.1 Pilot phase

Progression to the definitive trial will be based on the following outcomes:

- 80% of healthcare providers adhering to critical steps of the pulse oximetry use guidelines (combination of WHO and manufacturer guidelines provided as part of intervention), assessed using the SPA observation in pilot facilities
- 80% of eligible children recruited
- 90% of caregivers reachable by phone on Day 7 for outcome assessment

If these outcomes are not met during the pilot phase, the research steering committee will review and advise on adjustments and progress to the definitive trial.

Furthermore, the following outcomes will be assessed in order to verify sample size assumptions:

- Attendance rate of eligible children per month attending study
- Primary outcome proportions in routine care

If a deviation from the original assumptions are substantial, sample size calculations and recruitment strategies will be reviewed and modified if necessary.

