3.4 Sample Size

The sample size for the pragmatic RCT is calculated separately for each country, based on the following assumptions:

- ξ power of 80%
- ξ alpha level of 0.05 per arm
- ξ intra-cluster correlation coefficient (ICC) of 0.001
- ξ 1.1% severe complications in the control arm
- ξ 1.5% appropriate hospitalisations (within 24 hrs of Day 0 and as a results of referral) in the control arm

In India, initial sample size calculation for the three arm trial was based on having the power to detect a 30% or greater decrease in severe complication and 30% or greater increase in appropriate hospitalisation for each arm compared to control with 40 cluster per arm. This assumes average recruitment of 510 children per cluster over the 12 month period (total 40800), with an average of 110 per CHC per month and 20 children per PHC, assuming an average facility ratio CHC : PHC of 1:3. Following the decision, based on the pilot, not to introduce the CDSA, facilities were reallocated to the remaining two arms up to 60 facilities per arm.

In Tanzania, the study would have the power to detect a 30% or greater decrease in severe complication and a 30% or greater increase in appropriate hospitalisation for each arm compared to control with 22 clusters per arm. This assumes average recruitment of 1680 children per cluster over the 12 month period (total 110880), with an average of 350 children per health centre per month and 70 children per dispensary per month, assuming an average facility ratio health center : dispensary of 1:3.

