6.2.4 Pre-planned Sensitivity Analyses

Sensitivity analyses on the primary outcomes are planned and will be conducted:

- ξ On first encounters, which will include only the first enrolment episode of each child during the study period (as some children may attend the facility on more than one occasion). Separate presentations are identifiable from Day0 form as the caregiver is asked whether the child attended previously and within 28 days. This is the minimum number of days required for the disease episode to be considered a new one and not a repeat visit.
- ξ Looking at different hospitalisation appropriateness (based on different definitions of primary and secondary hospitalisations). Same day (Day0), 3 days and 7 days from Day0 will be used as cut-offs for different primary and secondary hospitalisation definitions.
- ξ Looking at different referral definitions:
 - ο A child will be considered to be referred if, at Day0, caregiver confirms that the child was urgently referred *and* the research assistant confirms that an urgent referral advice was recorded for the child².
 - ο A child will be considered to be referred if, at Day0, the research assistant confirms that an urgent referral advice was recorded for the child. If urgency is unknown, referral will be assumed to be urgent.

Additionally, a set of sensitivity analyses on the primary outcomes shall be carried out in case of substantial missing data (e.g. >10%) to evaluate the impact of each method on the primary outcomes results and take them into account when interpreting the final analysis results. Planned methods will include:

- ξ Worst case scenario
- ξ Complete cases
- ξ Multiple imputations with chained equations [11, 12]

Details of the methods are provided in Section 6.3.

Sensitivity analyses will only be performed for the final statistical analysis and not for interim analyses and DMC reports.

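### The single worst-case rule for lost children dilutes the severe-complication comparison, is undefined for appropriate hospitalisation, and leaves loss that differs informatively by arm untested

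*SAP*

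**What the plan says.** SAP 6.3 sets the primary handling of missing outcomes: "The primary analysis will be performed assuming the best case scenario (alive and not hospitalised) for children lost to follow-up or withdrawn". Further analyses follow "in case of substantial missing data on the primary outcomes (e.g. >10"%). SAP 6.2.4 lists three, for the primary outcomes jointly: "Worst case scenario", complete cases, and multiple imputation. SAP 6.3 defines the first in one line: "children lost to follow-up or withdrawn will be assumed as dead or hospitalised". It names no arm and no outcome, and it does not say whether the assumed hospitalisation is primary or secondary. The multiple-imputation item in the same list does separate those two types.

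The two outcomes point in opposite directions. Severe complication (SAP 6.1.2.1) counts death, delayed hospitalisation and hospitalisation without referral, and should fall. Appropriate hospitalisation (SAP 6.1.2.3) should rise, and it counts an admission only if the child was referred at Day 0 and admitted by the end of the next day.

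The planning values are "1.1% severe complications in the control arm" and "1.5% appropriate hospitalisations (within 24 hrs of Day 0 and as a results of referral) in the control arm". The Protocol summary gives the target as a "30% reduction in the severe complication primary outcome (from 1.1% to 0.77%) with 80% power".

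**The concern.** A worst case is meant to show whether the conclusion survives an unfavourable assumption about children who were not seen. Two features of this rule work against that.

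- **Same value in all arms.** Giving every lost child the event in both arms is not unfavourable to the comparison. It adds a large, roughly equal block of events to each side. With an outcome near 1% and a trigger near 10%, the imputed block is far larger than the observed events.
- **One rule for two directions.** Being hospitalised is a bad result for severe complication and the hoped-for result for appropriate hospitalisation. The unfavourable value for the second outcome, not hospitalised, is what the primary analysis already assigns under the label of best case. The labels are reversed for that outcome.

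SAP 6.2.4 says these results will be weighed when the final analysis is interpreted, so an uninformative or ambiguous result would feed into the conclusions. Loss near the trigger is foreseeable: the pilot progression target in Protocol 6.4.1 was "90% of caregivers reachable by phone on Day 7 for outcome assessment".

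**Working it through.** **Inputs.** From SAP 3.4: control rates 1.1% and 1.5%, 30% effects (hence 0.77% and 1.95%), alpha 0.05, power 80%, ICC 0.001, 22 clusters of 1,680 per arm (Tanzania), and 40 clusters of 510 (initial India design), later up to 60. The documents give no loss rate. I take L = 10%, the trigger value, and show up to 20%.

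**Reproducing the plan.** With the pooled two-proportion formula, n = [1.96√(2p̄(1−p̄)) + 0.842√(p₁(1−p₁)+p₂(1−p₂))]² / (p₁−p₂)² = 13,351 per arm for 1.1% v 0.77%.
- India: design effect 1 + 509 × 0.001 = 1.509, giving 20,147 per arm, or 39.5 clusters. This rounds to 40 (power 80.5%). With 60 clusters of 510, power is 93.2%.
- Tanzania: design effect 1 + 1,679 × 0.001 = 2.679, giving 35,768 per arm, or 21.3 clusters. This rounds to 22 (power 81.3%).

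The stated cluster numbers reproduce.

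**Severe complication, equal loss.** Arm rate = (1−L)p + L.
- Control: 0.9 × 1.1% + 10% = 10.99%.
- Intervention: 0.9 × 0.77% + 10% = 10.69%.
- Odds ratio: (0.10693/0.89307) / (0.1099/0.8901) = 0.97, against 0.70 planned.
- Risk difference: −0.30 points, against −0.33 planned.
- Imputed share of control events: 10/10.99 = 91%. Imputed per observed event: 10/0.99 = 10.1 (control) and 10/0.693 = 14.4 (intervention).

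| L, both arms | OR | control events imputed | power (India 40 / India 60 / Tanzania) |
|---|---|---|---|
| 10% | 0.970 | 91% | 12% / 16% / 12% |
| 15% | 0.979 | 94% | 9% / 12% / 9% |
| 20% | 0.984 | 96% | 8% / 10% / 8% |

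For comparison at 10% loss, the primary (best-case) analysis has OR 0.70 and power 76% / 91% / 77%. Complete case has 78% / 92% / 80%.

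**Severe complication, unequal loss.**
- 10% control v 11% intervention, planned effect true: 0.89 × 0.77% + 11% = 11.69% v 10.99%, OR 1.07.
- Same loss, no true effect: 0.89 × 1.1% + 11% = 11.98% v 10.99%, OR 1.10 (z about 2.6 in Tanzania at ICC 0.001).
- Extra intervention-arm loss that cancels the planned effect: (10.99% − 0.77%)/(1 − 0.0077) − 10% = 0.30 points.

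**Appropriate hospitalisation, 10% loss.** Three readings are possible.
- (a) All lost children counted: 0.9 × 1.5% + 10% = 11.35% v 0.9 × 1.95% + 10% = 11.76%, OR 1.04. SAP 6.1.2.3 rules this out for unreferred children.
- (b) Only referred lost children counted. With assumed referral of 2% to 10% in control and 30% higher in intervention, rates run from 1.55% v 2.02% to 2.35% v 3.06%, OR about 1.31.
- (c) Lost children scored as dead or as secondary hospitalisation: 1.35% v 1.76%, OR 1.31, identical to the primary analysis.

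No reading gives a lost child a less favourable value than the primary analysis does.

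**Where the severe-complication effect disappears.** With 10% loss and 1.1% events among lost control children, the control arm is at 1.1%. The intervention arm equals it when 0.9 × 0.77% + 0.1x = 1.1%, so x = (1.1% − 0.693%)/0.1 = 4.07%. In odds, (0.0407/0.9593)/(0.0077/0.9923) is about 5.5 times the observed odds. The planned fixed assumptions are 0% or 100% in both arms together, so this region is not examined.

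**The case against.** The strongest defence is that this is one of three conditional sensitivity analyses and cannot alter the primary test. Complete-case analysis of the primary outcomes is planned in SAP 4.3 without the 10% condition. SAP 6.3 adds multiple imputation by treatment group and a description of missing data by arm, referral and severe disease. Day 28 data fill in for a missing Day 7 contact and in-person follow-up is offered, so the trigger may never be reached. With equal loss the risk difference, which the SAP also reports, barely moves. All of this stands, and it limits the weight of the point. It does not close the gap: complete case drops lost children and the imputation assumes loss at random, so neither tests informative loss that differs by arm.

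Three stronger readings are tempting, and the documents do not support them.

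- A reader might infer that the rule is simply the favourable case for appropriate hospitalisation. Unreferred lost children cannot enter that numerator, and readings (b) and (c) leave the odds ratio near the planned effect. Reading (a) dilutes it.
- A reader might infer that the analysis will nearly always show no effect. That assumes equal loss. A one-point imbalance can produce apparent harm, or apparent benefit if it runs the other way.
- A reader might infer that the rule tests nothing. It still gives an extreme upper bound on severe-complication rates and, under reading (b), a usable favourable bound for appropriate hospitalisation.

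**Conclusion.** The point holds in limited form. For severe complication, the all-events rule at trigger-level loss says little about the robustness of the between-arm comparison. Under equal loss it pulls the odds ratio to 0.97 with power of about 12–16%; under unequal loss it mostly reports the imbalance. For appropriate hospitalisation the rule is undefined, so two programmers could produce different results, and its label is reversed relative to the primary analysis.

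The figures assume that lost means no usable Day 7 or Day 28 contact, that every lost child is scored as a severe complication, that India keeps 510 children per cluster at 60 clusters, and that ICC 0.001 also applies to the imputed outcome. A higher ICC for loss would lower power further and shrink the z value. A referred lost child assigned an in-window admission would leave the severe-complication numerator, which is another consequence of not stating the type of hospitalisation. The 4.1% tipping value concerns the point estimate; statistical significance would be lost earlier.

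**What to change.** Amend SAP 6.2.4 and 6.3 as follows.

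1. State the unfavourable and favourable assumption separately for each primary outcome. Use the recorded Day 0 referral, so that only referred lost children can count as appropriately hospitalised.
2. Keep the all-events scenario, since Protocol 8.3.1 names worst-case handling among the possible approaches, but label it an extreme bound.
3. Add an arm-specific tipping-point (delta-adjusted) analysis for each outcome. Vary the event odds among lost children separately by arm, over a range wide enough to reach the point where the conclusion changes, and report that point. For severe complication at 10% loss the range must extend beyond about 5.5 times the observed odds in the intervention arm.

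No new data are needed. The cost is SAP wording and modest programming.
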